7.6.5.2 Confirmed Adjudicated Cardiovascular Adverse Events

The number and percentage of subjects with confirmed cardiovascular events (ie., heart failure as determined by the adjudication committee) will be summarized by preferred term and treatment group.

7.6.5.3 Confirmed Adjudicated Hepatic Adverse Events

The number and percentage of subjects with confirmed hepatic events (as determined by the adjudication committee) will be summarized by preferred term and treatment group. In addition, a listing of all adjudicated hepatic adverse events by subjects will be provided.

7.6.5.4 Other AEOSIs

Adverse events of special interest (AEOSI) will be defined based on lists of preferred terms. These lists will be reviewed and finalized prior to database lock and unblinding of the database.

The following summaries and listings of AEOSI will include all data regardless of use of rescue medication:

- AEs of genital infection
- AEs of genital infection by gender
- AEs of Urinary Tract Infection (UTI)
- AEs of UTI by gender
- AEs of renal impairment/failure
- AEs of volume depletion
- AEs of fracture
- AEs of hepatic disorder
- AEs of hypersensitivity reactions
- AEs of severe cutaneous adverse reactions
- AEs of gastroenteritis and upper respiratory tract infections
- AEs of decreased lymphocyte count
- AEs of pancreatitis
- AEs of all malignancies
- AEs of cardiac failure
- AEs of DKA

The number and percentage of subjects with each of these events will be summarized by preferred term and treatment group in the short-term treatment period and in the combined ST+LT treatment periods.

The number and percentage of subjects with events of urinary-tract infection will be summarized for the subgroups defined on the basis of categorized variables including incidence (1, 2, 3 or > 3). A similar summary will be produced for events of genital infection.

7.6.6 Laboratory Evaluation

Unless otherwise specified, laboratory data obtained after the start of study medication dosing up to and including 4 days (30 days for liver function laboratory tests) after the last short-term dosing date (or up to and including the start of the long-term treatment period, whichever comes first) will be considered as obtained during the short-term treatment period. Laboratory data obtained from the day after the last study medication + 4 days (30 days for liver function laboratory

tests) up to the last visit date of the follow-up period will be considered as obtained during the follow-up period. Laboratory data obtained after the start of ST treatment up to and including 4 days (30 days for liver function laboratory tests) after the last dose of ST or LT medication will be considered as obtained during the combined ST+LT treatment periods.

Listings for lab data will include everything in the database.

For liver safety, a summary of proportion of subjects with elevated liver test including elevated AT (ALT and/or AST) and total bilirubin (see Appendix 1 for definition) will be provided. In addition, a summary of proportion of subjects with elevated liver test and/or reported AE of hepatic disorder will also be provided.

All laboratory evaluations performed by central laboratories will be included in summary tables. All lab tables for the CSRs will be produced in both US and SI units whenever available.

7.6.6.1 Marked Laboratory Abnormalities

Laboratory abnormalities will be evaluated based on marked abnormality values (MA). The pre-defined criteria for marked abnormalities are detailed in Appendix 3. If both the baseline and on-treatment values of a parameter are beyond the same MA limit for the parameter, then the on-treatment value will be considered a MA only if it is more extreme (farther from the limit) than was the baseline value. If the baseline value is beyond the low MA limit, and the post-baseline value is beyond the high MA limit (or vice-versa), then the post-baseline value will be considered a MA.

Laboratory abnormalities occurring during the short-term treatment period and the combined ST+LT treatment periods will be summarized by treatment group. In the short-term treatment period the summaries will be presented for both the primary and sensitivity safety analyses. The direction of change (high or low) in MA will be indicated in the tables.

For each subject with an MA for a parameter, all the subject's values of that parameter will be listed.

7.6.6.2 Change from Baseline for Selected Laboratory Parameters Over Time

All analyses of laboratory data will use observed data regardless of rescue. Visit windows are provided in Section 8.3 in order to link each laboratory test to a scheduled visit. Change from baseline during the ST treatment period and the combined ST+LT treatment periods for selected laboratory parameters will be summarized descriptively by treatment group using n's, means, medians, SEs, and 95% CIs

- hematocrit
- hemoglobin
- platelet count
- white blood cell (WBC) count
- total bilirubin

- alanine aminotransferase (ALT)
- alkaline phosphatase
- aspartate aminotransferase (AST)
- Estimated GFR using MDRD equation:

$$\text{eGFR (mL/min/1.73m}^2\text{)} = 175 \times (\text{Scr})^{-1.154} \times (\text{Age})^{-0.203} \times (0.742 \text{ if female}) \times (1.210 \text{ if}$$

African-American)

- creatinine kinase (creatinine phosphokinase) (CK)
- creatinine, serum (Scr)
- electrolytes - sodium, potassium, chloride, magnesium and calcium
- total protein, serum
- albumin (CV181169 only)
- inorganic phosphorus
- urinary albumin to creatinine ratio
- creatinine clearance

7.6.7 Vital Signs

Vital signs data obtained after the start of study medication dosing up to and including 4 days after the last short-term dosing date (or up to and including the start of the long-term treatment period, whichever comes first) will be considered as obtained during the short-term treatment period.

Vital signs data obtained after the start of study medication dosing up to and including 4 days after the last ST or LT dosing date will be considered as obtained during the combined ST+LT treatment period.

Visit windows are provided in Section 8.3 in order to link each vital sign measurement to a scheduled visit. Values and changes from baseline for vital sign measurements will be summarized by treatment group at each scheduled visit using descriptive statistics (using available data regardless of rescue for subjects in Treated Subjects Data Set).

7.6.8 Electrocardiograms

The normality/abnormality of the ECG tracing, as determined by the investigator, will be summarized using frequency tables on number of subjects who have a normal/abnormal ECG tracing at Week 24 and at Week 52 by the ECG tracing at baseline.

7.6.9 Pregnancy Test Results

By-subject listings of pregnancy test results will be provided using Treated Subject Data Set for the ST and the combined ST+LT treatment periods.

8 CONVENTIONS

Data collected outside the analysis window (defined in Section 8.4) after subjects discontinued open-label study medication will be excluded from analyses.

8.1 Duration of Type 2 Diabetes

Duration of Type 2 diabetes is calculated as the number of years from Type 2 diabetes diagnosis date to informed consent date:

$$(1 + \text{consent date} - \text{diagnosis date}) / 365.25.$$

The duration of diabetes will be included in the baseline diabetes characteristics listing.

If the date Type 2 diabetes was diagnosed is partially missing, the following rules will take effect:

- Missing day, but month and year are present: the day will be imputed as the 15th day of the month.
- Missing day and month, but year is present: the day and month will be imputed as 30 June of the year (provided that the imputed date is less than the consent date).
- Missing year, but day and month are present: No imputations will occur, and the subject will be excluded from all summaries related to duration of Type 2 diabetes.
- Missing day, month and year: No imputations will occur, and the subject will be excluded from all summaries related to duration of Type 2 diabetes.
- If any such imputed date falls after the consent date, then the diagnosis date will be taken as equal to the consent date.

These durations, even if partially imputed, will be listed. However, only the portion of the date of diagnosis actually observed, rather than imputed dates, will be displayed in listings.

8.2 Missing and Multiple Measurements

For listings of efficacy and safety measures, missing values will be represented as not reported.

If the blood pressure measurements are taken at a wrong position, e.g., sitting instead of standing, then these measurements will be excluded from the summary/analysis.

Some laboratory samples may be inadvertently analyzed multiple times for the same test, producing multiple lab results on the same collection date and time for the same subject.

In case of multiple observations within a single visit window, the following rules apply:

- If there are two or more observations within the same visit window, the nonmissing observation closest to the target day will be used in the analysis

- If two observations are equidistant from the target day, the non-missing observation with the later collection date will be used in the analysis
- If two or more observations are collected on the same day and have a collection time associated with them, the non-missing observation with the later collection time will be used in the analysis
- If two or more observations are collected on the same day and time, all non-missing and the average of the observations will be used in the analysis.
- If two or more observations are collected on the same day, all non-missing but with no collection time associated with at least one of them, the average of the observations will be used in the analysis.

If a visit window does not contain any observations, the data will be missing for that visit.

8.3 Laboratory evaluations

All laboratory evaluations performed by central laboratories and local laboratories that are included in the database will be listed but only the data from central lab will be included in summary tables.

8.3.1 Post treatment efficacy and safety evaluations

While efficacy and safety observations will be listed regardless of whether the subject was taking open-label study drug, observations may not contribute to summaries/analyses if they are measured after the last dose of the open-label study medication given during the treatment periods, as indicated below:

For efficacy parameters:

- Lipids and metabolic surrogate markers will be summarized only if measured on or prior to the 4th day after the last study drug treatment date.
- FPG and spot urinary glucose to creatinine ratio will be summarized/analyzed only if measured on or prior to the first day after the last study drug treatment date.
- HbA1c and body weight will be summarized/analyzed only if measured on or prior to the 8th day after the last study drug treatment date.

For safety parameters:

- SAEs and the lab measurements for the liver function tests will be included in the summaries only if occurred/measured on or prior to the 30th day after the last study drug treatment date.
- All other safety events (non-severe AEs, hypoglycemia, etc) and measurements (safety lab, vital signs, etc) will be included in the summaries only if occurred/measured on or prior to the 4th day after the last study drug treatment date.

8.4 Longitudinal Assessments

Day 1 for the short-term treatment period is the start date of short-term treatment medication.

Visit windows are specified below.

Table 8.4-1: Visit Windows for the Short-term Analyses			
Visit	Treatment Period	Target Day	Day Range
Week 1	ST	8	2-10
Week 2	ST	15	11-22
Week 4	ST	29	23-43
Week 8	ST	57	44-71
Week 12	ST	85	72-106
Week 18	ST	127	107-148
Week 24	ST	169	149 to last day of short-term

Table 8.4-2: Visit Windows for the Short-term + Long-term analyses			
Visit	Treatment Period	Target Day	Day Range
Week 1	ST	8	2-10
Week 2	ST	15	11-22
Week 4	ST	29	23-43
Week 8	ST	57	44-71
Week 12	ST	85	72-106
Week 18	ST	127	107-148
Week 24	ST	169	149 - 197
Week 32	LT	225	198 - 252
Week 40	LT	281	253-324
Week 52	LT	365	325 to last day of long-term treatment

Table 8.4-3: HbA1c, Weight - Visit Windows for the Short-term analyses			
Visit	Treatment Period	Target Day	Day Range
Week 4	ST	29	2-43
Week 8	ST	57	44-71
Week 12	ST	85	72-106
Week 18	ST	127	107-148
Week 24	ST	169	149 to last day of short-term

Table 8.4-4: HbA1c, Weight - Visit Windows for the Short-term + long term analyses			
Visit	Treatment Period	Target Day	Day Range
Week 4	ST	29	2-43
Week 8	ST	57	44-71
Week 12	ST	85	72-106
Week 18	ST	127	107-148
Week 24	ST	169	149 -197
Week 32	LT	225	198 - 253
Week 40	LT	281	254-324
Week 52	LT	365	325to last day of long-term treatment

8.5 Post-Treatment Efficacy Observations

While short-term treatment period (up to and including the start of long-term treatment period, where applicable) efficacy observations will be listed regardless of whether the subject was taking study drug, observations may not contribute to summaries/analyses if they are measured after the last dose of short-term study medication (up to and including the start of long-term treatment period, where applicable) as indicated below:

- Lipids and metabolic surrogate markers will be summarized only if measured on or prior to the 4th day after the last study drug treatment date.
- FPG, fasting insulin, fasting C-peptide, and spot urinary glucose to creatinine ratio will be summarized/analyzed only if measured on or prior to the first day after the last study drug treatment date.
- HbA1c, body weight, BMI and waist circumference, will be summarized/analyzed only if measured on or prior to the 8th day after the last study drug treatment date.

Similar rule applies for the combined ST+LT treatment periods.

8.6 Assignment of Doses to Adverse Events and Laboratory Assessments

In case of missing dates, prior to assigning the treatment that the subject received at the onset of an AE or at the time of a laboratory assessment, imputation rules will be applied as follows:

For AEs, a missing or incomplete onset date will be imputed according to the following conventions:

- If the onset date for an AE is missing or incomplete, an imputed date will be derived to slot the event to an appropriate analysis period. This derived date will not be reported in summary tables or listings. Every effort will be made to determine the actual onset date for the event or to obtain a reliable estimate for the onset date from the investigator.
- If an onset date is missing, the derived onset date will be calculated as the first non-missing valid date from the following list (in order of precedence):
 - First active study medication date
 - Consent date
 - Visit date corresponding to the visit at which the event was reported.
 - If a valid non-missing date is not available for any of these dates, the derived onset date will be set to missing.
- If an onset date is incomplete, the derived onset date will be calculated using the following algorithm:
 - Calculate a surrogate date as the first non-missing valid date from the following list (in order of precedence):
 - First active study medication date
 - Consent date
 - Visit date corresponding to the visit at which the event was reported
 - If a valid non-missing date is not available for any of these dates, the surrogate date will be set to missing.
 - Based on the information provided, set the derived date to the earliest possible date. If only a year is provided, set the derived date to January first of that year. If a year and month is provided, set the derived date to the first day of that month.
 - If the surrogate date is non-missing then:

- If the derived date is on or after the surrogate date use the derived date as calculated
 - If the derived date is prior to the surrogate date and the surrogate date is consistent with the partial data provided for the onset date, use the surrogate date as the derived date
 - If the derived date is prior to the surrogate date and the surrogate date is not consistent with the partial data provided for the onset date then set the derived onset date to be the latest possible date based on the partial onset date information provided. If only a year is provided, set the derived date to December 31st of that year. If a year and month is provided, set the derived date to the last day of that month.
- If all three dates used to determine the surrogate date are missing, then based on the information provided, set the derived date to the earliest possible date. If only a year is provided, set the derived date to January first of that year. If a year and month is provided, set the derived date to the first day of that month.

A drug treatment file will be created, containing any starting and stopping dose as well as intermediate dose changes within each study period, with dates as recorded on the CRF. In this context,

- The date of the first dose of study medication is defined as the earliest start date with number of tablets > 0 reported on the study medication page.
- date of the last dose of study medication is defined as the latest start or stop date with number of tablets > 0 reported on the study medication page.

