7.6.1.1 All Adverse Events

An overall summary of adverse events at subject level, including AEs, SAEs, death, hypoglycemia, treatment-related events and events leading to the discontinuation of study medication will be performed for the short-term treatment periods. All adverse events (serious and non-serious, excluding hypoglycemic events that are not reported as SAEs) will be summarized by system organ class, preferred term for the short-term treatment periods. For the analyses of the short-term treatment period, the summary of AEs and analyses by SOC and PT will be performed for the primary and sensitivity safety analyses. In addition, a subject listing of all reported adverse events will be produced, displaying all events (including pre-treatment events) that occurred prior to the start date of long-term treatment period, if any. All adverse events (serious and non-serious) including all hypoglycemic events will also be summarized by treatment group, where applicable.

AEs and SAEs with an onset from Day 1 of short-term treatment up to and including 4 days and 30 days respectively, after the last dose date in the short-term treatment period (or up and including to the start date of the long-term treatment period whichever comes first) will be considered as occurring during the short-term treatment period.

In addition, the following summaries will be provided for the short-term treatment period (excluding hypoglycemic events that are not reported as SAEs):

- Most common adverse events by preferred term and treatment group (i.e., reported by ≥ 2 % of subjects in any treatment group),
- Adverse events by system organ class, preferred term, intensity and treatment group,

- Adverse events related to study medication by system organ class, preferred term and treatment group.
- Proportion of subjects with adverse events by SOC and PT in subgroups of subjects defined by age category (< 65 and ≥ 65 yrs), gender, race, and female age category (≤ 50 and > 50 yrs).

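### The AE onset-date rule in SAP 8.6 moves missing and compatible partial dates to first dose, even when a recorded resolution or reporting date shows the event was pre-treatment

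*SAP*

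**What the plan says.** SAP section 8.6 states the aim of the imputation: "an imputed date will be derived to slot the event to an appropriate analysis period".

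For a fully missing onset the rule is: "If an onset date is missing, the derived onset date will be calculated as the first non-missing valid date from the following list". The list has three entries. The first is "First active study medication date", the second is the consent date, and the third is "Visit date corresponding to the visit at which the event was reported".

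For a partial onset, the first available date in the same list becomes a surrogate, and the earliest date that the partial information allows is compared with it.
- If that earliest date is on or after the surrogate, it is kept.
- If it is before the surrogate but the surrogate fits the known month or year, the surrogate is taken: "the surrogate date is consistent with the partial data provided for the onset date, use the surrogate date as the derived date".
- If the surrogate does not fit, "then set the derived onset date to be the latest possible date based on the partial onset date information provided".

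Section 8.6 also promises an effort to obtain the true date, or a reliable estimate, from the investigator. It says that the derived date is not shown in tables or listings.

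Sections 7.6.1.1 and 7.6.5 count AEs, and AEs of special interest, as on-treatment when their onset falls from Day 1 onward. The AE listing in 7.6.1.1 is described as "displaying all events (including pre-treatment events) that occurred prior to the start date of long-term treatment period", so events from before treatment are in the database. The same section uses resolution dates to separate new from continuing events, so those dates are collected.

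**The concern.** Sending an onset of unknown timing to first dose is a common cautious convention. It is justified because nothing on record places the event elsewhere. Section 8.6 applies it without asking whether something does.

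An event that ended in the lead-in period, or was reported at a lead-in visit, cannot have begun on treatment. If its onset date is missing or fits the first dose date, the rule still gives it a Day 1 onset. That defeats the section's own purpose of putting each event in the right period. At stake is the accuracy of the on-treatment AE and special-interest counts. Because the derived date is not displayed, a reader could not see why such an event was counted.

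**Working it through.** The SAP gives no figure to reproduce here, so the check is to apply the rule literally.

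**Rule.** Let S be the first available of first dose, consent and reporting visit. For a partial date, let L and U be its earliest and latest possible values.
- Missing onset: derived onset = S.
- Partial, L ≥ S: derived onset = L.
- Partial, L < S ≤ U: derived onset = S.
- Partial, U < S: derived onset = U.

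The Treated Subjects Data Set (6.3.6) requires at least one dose. For any treated subject with a recorded first dose date, S is therefore that date. The resolution date appears in no branch, and the reporting visit appears only as the third fallback.

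**Illustrative dates (assumed):** consent 10 February 2016, lead-in visit 8 March, first dose 20 March.

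| Recorded onset | Other record | Derived onset | Placed | Against resolution |
|---|---|---|---|---|
| Missing | Reported and resolved 8 March | 20 March | On-treatment | 12 days after |
| March 2016 | Resolved 10 March | 20 March | On-treatment | 10 days after |
| 2016 only | Resolved 1 March | 20 March | On-treatment | 19 days after |
| February 2016 | Resolved 1 March | 29 February | Pre-treatment | Consistent |
| April 2016 | Resolved 30 April | 1 April | On-treatment | Consistent |

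The first three rows are wrong and the last two are right.

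**How often a partial date is moved.** Assume that the true onset is uniform over the w days before first dose, and that first dose is uniform over a 366-day year. A month-and-year onset moves to first dose when both dates fall in the same calendar month. On average (w + 1)/2 first-dose days per month are lost to the previous month, so the share moved is 1 − 12 × [(w + 1)/2] / 366.
- w = 14: 1 − 12 × 7.5/366 = 276/366 = 75%.
- w = 28: 1 − 12 × 14.5/366 = 192/366 = 52%.

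For a year-only onset the loss occurs once a year, so the share is 1 − [(w + 1)/2] / 366.
- w = 14: 358.5/366 = 98%.
- w = 28: 351.5/366 = 96%.

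These shares apply only to pre-treatment events with partial dates. The defect also needs a resolution or first reporting date before first dose. The SAP does not say how many such events there are.

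**Insulin glargine.** Section 8.6 defines the first dose as the earliest study-medication record with more than zero tablets. If an insulin subject had no such record, S would fall to consent, 10 February. A missing onset would become 10 February and March 2016 would become 1 March, both pre-treatment.

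**The case against.** The strongest reply is that this is an explicit, reproducible convention that errs towards counting events as on-treatment, that queries come first, and that few dates will stay incomplete. All of that stands, and it keeps the point minor. It does not answer the gap. The algorithm exists for dates that queries leave unresolved, and caution has no purpose where a recorded date settles the timing. The last branch already keeps partial dates wholly before first dose as pre-treatment, so the SAP accepts the principle.

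A reader might infer more than the documents support:
- *Every pre-treatment event with a missing or compatible onset is demonstrably misplaced.* No. If it was still ongoing at first dose and first reported afterwards, nothing on record contradicts the default.
- *The consent and visit entries can never be used.* That holds only where a first dose date is recorded, which the tablet-based definition leaves open for insulin.
- *The treatment comparison is distorted.* Section 7.6.1.1 plans no formal comparison of AEs, and events that precede randomized treatment should be balanced by randomization.
- *The tables of related events are inflated.* Relationship is the investigator's assessment, and nothing suggests that an event over before dosing would be judged related.
- *Output will show onsets later than resolutions.* The derived date is not displayed.
- *Special-interest counts will visibly change.* Nothing in the SAP shows this.
- *The rule acts differently by arm because of the tablet definition.* Section 7.4.3 counts the days on which insulin was taken, so dosing dates appear to be recorded. The wording needs reconciling, but an actual arm difference is not established.

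**Conclusion.** The point holds as a small defect in a stated rule. Once queries have failed, a missing onset, or a partial onset whose known month or year contains the first dose date, becomes Day 1 even when the recorded resolution or first reporting visit is before first dose. For those events the misclassification follows directly from the text, provided the subject has a first dose date.

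The size is probably small and cannot be taken from the SAP. As an assumption only, if 0 to 1% of about 598 subjects had one such event, the count would be 0 to 0.01 × 598 ≈ 6, spread over two arms and all AE terms. No efficacy result is touched and no bias between arms is shown.

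**What to change.** Add to section 8.6, ahead of both algorithms: if the resolution date (its latest possible value when partial) or the date of the visit at which the event was first reported is before the first dose date, the event is pre-treatment. Its derived onset is the earlier of those two dates, or the latest date compatible with the partial onset if that is earlier still. Otherwise 8.6 applies as written.

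In the first three rows of the table, taking the reporting visit as no earlier than resolution, this gives 8 March, 10 March and 1 March, all pre-treatment. An event reported on the first dose date itself keeps the present default.

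State also how the first dose date is derived for insulin glargine subjects, since the tablet count does not describe them and the new check depends on that date.

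The cost is a sentence or two in the SAP and one programming condition, using dates already collected. No other analysis changes.
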